IRB Study Number: 20160951
Version #11; 7-18-2022

**RANDOMIZED, DOUBLE-BLINDED, CONTROLLED
TRIAL OF EARLY-INTERVENTION TENS
FOR THE REDUCTION OF THE PREVALENCE AND
SEVERITY OF CHRONIC NEUROPATHIC PAIN
DURING THE FIRST YEAR AFTER
SPINAL CORD INJURY**

IRB Number: 20160951
Protocol Version Number: 0.11
Protocol Version Date: 7/18/2022
PI Name: [name]
NCT Number: NCT03267810

1) Protocol Title

Randomized, double-blinded, controlled trial of early-intervention TENS for the reduction of the prevalence and severity of chronic neuropathic pain during the first year after spinal cord injury (SCI)

2) Objectives*

The primary objectives of our site-specific project are to test a non-invasive, non-pharmacologic, inexpensive intervention (i.e., transcutaneous electrical nerve stimulation; TENS) to prevent the development and reduce the severity of chronic neuropathic pain in the first year post-spinal cord injury (SCI) (Aim 1), and to increase the understanding of the time-course of the development of chronic neuropathic pain and the factors that increase the risk for neuropathic pain onset or worsening by longitudinally tracking pain symptoms, somatosensory function, and key injury-related and psychosocial factors during the first 12 months post-SCI (Aim 2).

Aim 1: Assess the effectiveness of preemptive/early-intervention TENS therapy to decrease the risk of developing chronic neuropathic pain, and to reduce the severity of neuropathic pain, following SCI.

Hypothesis 1a: Enhanced somatosensory stimulation using TENS within preserved dermatomes at or above the neurological level of injury will reduce the prevalence and severity of chronic neuropathic pain at 12 months post-injury when compared with neuropathic pain in those who receive Sham TENS.

Hypothesis 1b: Subjects for whom TENS effectively reduces evoked pain sensations (i.e., increased pain thresholds and/or decreased ratings of perceived intensity of noxious suprathreshold stimuli) at, and including three levels below, the level of injury after an 8-week TENS treatment protocol will be less likely to report chronic neuropathic pain

symptoms at 12 months post-injury than subjects for whom TENS does not reduce evoked pain sensations.

Aim 2: Evaluate demographic, psychological, and physiological characteristics that are potential risk factors for the development and severity of chronic neuropathic pain at 12 months post-injury.

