to determine their predictive ability for the presence and severity of neuropathic pain at 12 months post-injury (Hypothesis 2b). In addition, we will also collect these assessments at three other time points (approximately 4-6 months and 12 months post-injury), in order to explore the time-course of changes in these variables and their interrelationships with pain during the first year post-injury.

STT and DC-MLS dysfunction as risk factors for neuropathic pain (Physiologic risk factors):

Investigations examining the relationship between the presence of chronic neuropathic pain and injury severity (i.e., complete vs. incomplete)^{15, 21, 69-71} or radiologic evidence of the extent of damage to the spinal cord⁷² have generally reported negative findings. These investigations were unable to link severity or location of the spinal cord lesion to neuropathic pain, suggesting that these factors are only marginally related to the presence of neuropathic pain, or that these measurement tools are *too crude* to reveal an association.

Several studies have used more sensitive quantitative sensory testing (QST) techniques to identify the potential contributions of STT and DC-MLS damage to the presence and severity of chronic neuropathic pain after SCI.^{6-8, 69, 73-76} Although results across these studies seem to suggest that lower levels of impairment within the STT are linked to increased severity of neuropathic pain,^{6, 7, 74} the cross-sectional nature of the data does not provide insight with regards to whether STT dysfunction is the cause, or result, of chronic neuropathic pain after SCI.

A few recent studies have approached this question by investigating longitudinal changes in somatosensory function and pain after SCI.^{5, 21, 42, 76} Of these studies, only one has used QST techniques to track STT and DC-MLS function across time after SCI in 30 subjects,⁴² while the others utilized less sensitive bedside sensory exams.^{5, 21, 76} Although details of the results from these studies differ, overall findings generally point to early post-injury sensitivity to evoked pain (pin prick or cool stimulus) as a predictor for the later development of neuropathic pain,^{5, 21, 42, 76} though the QST study additionally reported a relationship between higher thermal detection thresholds (i.e., *decreased* sensitivity to detecting non-painful changes in temperature) and development of neuropathic pain.⁴²

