Modality	SCI		Nondisabled	
	ICC (95% CI)	# total test sites	ICC (95% CI)	# total test sites
Log MDT	0.84 (0.75-0.90)	56	0.63 (0.45-0.76)	58
Log VDT	0.90 (0.84-0.94)	67	0.86 (0.79-0.91)	80
Log CDT	0.90 (0.83-0.94)	55	0.68 (0.54-0.78)	80
Log WDT	0.95 (0.91-0.97)	50	0.70 (0.57-0.80)	79
CPT	0.50 (0.28-0.67)	56	0.49 (0.31-0.64)	80
HPT	0.50 (0.28-0.66)	62	0.68 (0.55-0.79)	79

MDT = mechanical detection threshold; VDT = vibration detection threshold; CDT = cool detection threshold; WDT = warm detection threshold; CPT = cold pain threshold; HPT = hot pain threshold

severity of chronic neuropathic pain symptoms, in participants with chronic SCI.^{6, 8, 74} **Figure 4** shows that, in test sites in body areas where neuropathic pain symptoms were present, lower pain thresholds (i.e., increased pain sensitivity) were associated with more severe neuropathic pain scores.

Thus, previous work by the study investigators demonstrates that the study is feasible and that they have the skills and tools necessary to perform the proposed study. Results from this body of work support the rationale of the proposed site-specific study.

Figure 4: Pain threshold is negatively related to severity of NeuP in those with SCI

Subjects with SCI and NeuP ($n = 22$) completed sensory testing at sites within the area affected by NeuP. Thresholds were also obtained in control subjects at the same test sites on the body and used to calculate z-scores for the thresholds obtained in those with SCI. Subjects with less loss of pain sensation (z-scores close to 0) had significantly higher NPSI scores than those with greater loss of pain sensation (higher z-scores).⁷⁴ (Z-scores reflect the degree to which thresholds in participants with SCI vary from the distribution of thresholds obtained in nondisabled control subjects, and allow for comparison of measures obtained at different locations on the body.)

4) Inclusion and Exclusion Criteria*

Inclusion criteria:

- Age ≥ 18 ;
- Traumatic spinal cord injury;
- Date of injury occurring within four months of study enrollment.

Exclusion criteria:

- More than four months since date of injury;
- Contraindications for the study intervention, transcutaneous electrical nerve stimulation (TENS),⁸⁸ including:
 - Implanted electronic device such as a pacemaker;
 - Cardiovascular problems;
 - Pregnancy;
 - Epilepsy;
 - Cancer;
- Persons with a spinal cord injury at the C2 level, as placement of TENS electrodes on the neck is not recommended;

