(c) Electrode placement: Surface electrodes are typically placed in the area overlapping the pain. However, because persons with SCI may have reduced or absent sensory function in these areas due to their injury, and, because the goal of the study is to *prevent* pain (i.e., the majority of our subjects will not have developed any area of neuropathic pain when they are initially enrolled in the study) we will place electrodes according to neurological level of injury, so that the location of all electrodes fall within the dermatome of the level of injury or the dermatome just above the level of injury, as described in Norrbrink's study,³⁵ in order for stimulation to occur in a location where normal sensation is present.⁸⁸ Two electrodes from one channel will be placed paraspinally at the level of injury. The other channel's two electrodes will be placed at distal aspects within the same dermatome (at the level of injury) except for subjects who do not have appropriate skin locations available (e.g., due to presence of skin lesions/damage, or levels of injury with limited accessible skin surface area). Both stimulation channels will be set with the same stimulation parameters. If adjustments are needed to positioning of the electrodes outside of the prescribed area (at the level of injury or one dermatome above the level of injury), consideration of best placement will be discussed among the research and clinical study team on

a case-by case basis.

(d) *Sham TENS parameters*: Electrode placement for subjects randomized to Sham TENS will be based on their level of injury as described above for those in the TENS group. At the beginning of each session, the stimulus will be turned up until the subject just reports sensation (as with the TENS group), but then will be adjusted down so that no electrical stimulus is delivered.

Data collected / Assessments performed:

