symptoms at the 12 month post-injury time point. It is anticipated that those who show reduced sensitivity to noxious stimuli after TENS treatments will exhibit a lower risk for chronic neuropathic pain. A repeated measures regression analysis, including appropriate covariates (e.g., demographic and injury-related factors, concomitant treatments, amplitude setting of TENS treatments), will assess whether changes in evoked pain sensitivity will be a significant predictor of neuropathic pain at 12 months post-injury in the TENS treatment group.

Hypotheses 2a, 2b, and 2c:

Chi square analyses, t-tests, and correlations across all subjects (with TENS group assignment as a covariate) will be used to separately examine whether demographic variables (age and minority status), psychological characteristics (pain catastrophizing, depressive symptoms severity, and levels of resilience), and measures of evoked pain sensitivity (pain thresholds and ratings of suprathreshold noxious stimuli) measured at baseline can predict the presence and severity of chronic neuropathic pain at 12 months post-SCI. Separate sub-analyses will also be conducted with regard to the impact of these factors on pains with different diagnostic categories (nociceptive pain, neuropathic pain).

Data security / Quality control:

All research personnel will complete and maintain trainings regarding privacy and data security as required. All personnel will receive training regarding all study procedures as required for their role, as assigned and overseen by the PI, to insure data quality and integrity of the science.

Data for the study will be recorded on paper, using the most-updated and approved study forms. These paper documents will be stored in locked file cabinets in rooms 3.156 and 3.153B of the Christine E. Lynn Rehabilitation Center ([name]). This room is locked and is accessible only by those who have been given card access. These paper documents will be stored for at least 3 years after the final termination of the grant.

Data from the paper documents will be entered into a password protected electronic database that will receive periodic and thorough data quality checks through established procedures. This

electronic file will not contain any personally-identifiable information, and will be maintained for at least 3 years after the final termination of the grant.

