c. During questionnaires, participants will be reminded that they can refuse to answer any questions that they feel are emotionally upsetting. If a participant indicates that he or she has suicidal ideations, the psychologist will be notified immediately. The risk frequency is low and the severity of mild to moderate, although all of the subjects will have already consented to participate in data collection from the SCIMS, and therefore would have already answered similar questions.

d. The PI will be responsible for administering testing using the TSA-II and for training any other study staff who will perform assessments with this device. She has 17 years of experience with the equipment that will be utilized in the proposed study (TSA-II; Medoc, Ltd.), including 12 years of experience using the equipment to test individuals with spinal cord injuries. The TSA-II has cut-off temperature values (0°C, 50°C) that are built-in limitations of the equipment. This prevents the machine from delivering stimuli that could potentially cause tissue damage. The short duration of stimulus presentations in this study (up to a maximum of 5 seconds per trial) will also limit any lasting effects of noxious stimulation. Temperatures in the ranges to be presented in the proposed study have been used by our laboratory for several years, including in individuals with spinal cord injury, with no adverse events other than nonpainful slight reddening of the skin that lasted for approximately 60 minutes. In addition, any severe anxiety or discomfort reported by the subject will be grounds for termination of the study session.

15) Potential Benefits to Subjects*

The primary benefit of this interventional study is the potential reduction or elimination of chronic neuropathic pain in subjects randomized to the TENS treatment arm. There is no anticipated benefit for subjects randomized to the sham TENS arm. In addition, no direct benefit can be promised to those in the TENS treatment group, as this is an experimental intervention for prevention of neuropathic pain in this patient group.

16) Vulnerable Populations*

No vulnerable populations will be recruited or enrolled in the study.

17) Sharing of Results with Subjects*

Results of the study assessments will not be routinely disclosed to research subjects. However, study staff will discuss results with those subjects who specifically ask for information from their assessments.

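### Hypothesis 1b relates the change in evoked pain to 12-month neuropathic pain without conditioning on baseline evoked pain, which the protocol treats as a predictor of that pain and which limits how far evoked pain can fall

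*Combined protocol and SAP*

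**What the plan says.** Section 2 (Objectives) words Hypothesis 1b as a comparison of two kinds of subject: "Subjects for whom TENS effectively reduces evoked pain sensations", through higher pain thresholds or lower ratings of noxious stimuli at the injury level and the three levels below it, are expected to have less chronic neuropathic pain at 12 months "than subjects for whom TENS does not reduce evoked pain sensations". There is no third category for subjects with no evoked pain to reduce.

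Section 11 (Hypothesis 1b) plans something different. It correlates the before-to-after change in evoked pain with the presence and severity of neuropathic pain at 12 months. It then fits a repeated measures regression in the TENS arm with that change as the predictor, "including appropriate covariates (e.g., demographic and injury-related factors, concomitant treatments, amplitude setting of TENS treatments"). No responder cut-off is defined, and no rule covers values at a measurement limit.

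Three other places bear on this:

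- Section 3 (Background, physiologic risk factors) says that earlier longitudinal studies point to "early post-injury sensitivity to evoked pain (pin prick or cool stimulus) as a predictor for the later development of neuropathic pain". Hypothesis 2c rests on the same idea, and its analysis in Section 11 uses baseline evoked-pain sensitivity as a predictor.
- Section 14 (Risks) says "The TSA-II has cut-off temperature values (0°C, 50°C) that are built-in limitations of the equipment".
- Section 9 schedules quantitative sensory testing at every full assessment, including baseline and end of treatment, so the baseline values will exist.

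**The concern.** A hot pain threshold already at 50°C cannot rise, a cold pain threshold already at 0°C cannot fall, and a rating at the floor cannot drop. A subject in that position at baseline contributes no reduction, whatever TENS does. If baseline sensitivity also predicts 12-month pain, as the protocol expects, it is tied both to the room for change and to the outcome. The planned correlation then mixes two questions: whether a fall in evoked pain goes with less later pain, and whether subjects who began with evoked pain differ in risk from those who did not.

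At stake is the reading of Hypothesis 1b as evidence on who responds to TENS. The primary comparison of arms is not affected.

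**Working it through.** **The plan's own figure.** Section 11 states that 41 subjects within a group give power 0.80 for an effect size f² of 0.20 at two-sided alpha 0.05. With the noncentral F test and one predictor, the noncentrality is f² × n = 0.20 × 41 = 8.2 on 1 and 39 degrees of freedom, and power is 0.797. The figure reproduces. It corresponds to a correlation of √(0.20/1.20) = 0.41.

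**Inputs not in the documents.** These are the share f of subjects with no evoked pain at baseline, their 12-month risk, the risk in the remaining (sensate) subjects, and the mean change in evoked pain among the sensate. All are assumed below.

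**The planned analysis (correlation with change).** Let the reduction have mean m and SD 1 in sensate subjects and be 0 in the others. Let reduction have no true effect, and let risk be p_S in sensate subjects and p_F in the others. Then

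- covariance = f(1−f) × m × (p_S − p_F)
- variance of the reduction = (1−f) + f(1−f)m²
- overall risk p = (1−f)p_S + f p_F, with variance p(1−p).

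With f = 0.30, p_S = 0.40 and p_F = 0.10, p = 0.31 and p(1−p) = 0.2139. For m = 0.5 the covariance is 0.0315, the variance of the reduction is 0.7525, and the correlation is 0.0315/√(0.7525 × 0.2139) = 0.08.

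| Mean reduction in sensate subjects | Spurious correlation of reduction with pain | Direction |
|---|---|---|
| 1 SD | +0.14 | against Hypothesis 1b |
| 0.5 SD | +0.08 | against |
| 0 | 0 | none |
| −0.5 SD (evoked pain rises) | −0.08 | in favour |

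Beside the 0.41 that the analysis is sized to detect, 0.08 to 0.14 is about a fifth to a third (0.08/0.41 = 0.20; 0.14/0.41 = 0.34).

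**With a true effect.** A large-sample logistic simulation (400,000 subjects, true slope −0.30, f from 10% to 40%) gave these slopes without baseline in the model: −0.23 to −0.14 if evoked pain falls by 0.5 SD on average, −0.27 to −0.31 if the mean change is zero, and −0.30 to −0.45 if it rises by 0.5 SD. With baseline in the model the slope was −0.29 to −0.30.

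**The two-group wording of Section 2.** Suppose half of sensate subjects reduce, with risk 30% in reducers and 50% in sensate non-reducers. Risk among all who show no reduction is [0.5(1−f) × 0.50 + f × p_F]/[0.5(1−f) + f]. For f = 0.20 and p_F = 0.10 this is (0.20 + 0.02)/0.60 = 36.7%, so the true difference of −20 points appears as −6.7.

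| f | Difference, p_F = 10% | Difference, p_F = 30% |
|---|---|---|
| 10% | −12.7 | −16.4 |
| 20% | −6.7 | −13.3 |
| 30% | −1.5 | −10.8 |
| 40% | +2.9 | −8.6 |
| 50% | +6.7 | −6.7 |

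**Cost of a remedy.** Five added covariates leave 34 residual degrees of freedom and power 0.794. Restricting to sensate subjects leaves 33 subjects at f = 20% (power 0.702) and 25 at f = 40% (power 0.572).

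**The case against.** The strongest reply is that the analysis section has no class of non-reducers. It uses change as a continuous predictor, and a subject without evoked pain enters with zero change. That is right, and it is why the direction of bias depends on the mean change in the others. A reader might infer from Section 2 alone that the contrast is simply biased against the hypothesis; the planned analysis does not support that without the further condition that evoked pain falls on average.

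A reader might also infer that subjects without evoked pain have low risk. No figure says so. The Background supports lower risk only in qualitative terms. It also reports generally negative findings for complete against incomplete injury, and one study in which poorer detection of non-painful temperature change went with developing neuropathic pain. The Figure 4 result, "Subjects with less loss of pain sensation (z-scores close to 0) had significantly higher NPSI scores than those with greater loss", comes from 22 people who all had neuropathic pain already, so it speaks to severity and not to risk.

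Nor does the electrode placement text in Section 9 show that the test region is often insensate. When it says that "persons with SCI may have reduced or absent sensory function in these areas due to their injury", it means the area overlapping the pain. The same sentence places electrodes at or just above the injury level because sensation there is normal, and the Hypothesis 1b region includes the injury level.

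Finally, the covariate list is open and includes injury-related factors, so baseline adjustment is unspecified rather than excluded. And because the regression uses the TENS arm alone, spontaneous recovery that lowers both evoked pain and later pain would push towards the hypothesis.

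All of this limits what can be said about direction and size. It does not remove the confounding. An unknown sign is a reason to name the covariate in advance.

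**Conclusion.** The concern holds in a limited form. As planned, the Hypothesis 1b association is confounded by baseline evoked-pain sensitivity, because the protocol itself makes that a predictor of the outcome and because measurement limits tie it to the possible change. If evoked pain falls on average, which is what the hypothesis supposes TENS to do, and subjects without evoked pain have lower risk, this mechanism works against the hypothesis. If the mean change is zero it is nil, and if evoked pain rises it is reversed. The net direction, with spontaneous recovery included, cannot be settled from the documents.

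Under the assumptions shown, the spurious correlation is modest (up to 0.14 at a 30% share). A reader might infer that a true protective association would change sign. In the tables above that happens only for the two-group contrast, with 10% risk in subjects without evoked pain and a share of at least 40%; with 30% risk it shrinks but never reverses. This is a secondary hypothesis, and the correction is worth making because the better model uses data already collected.

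**What to change.** In Section 11, Hypothesis 1b, make the main analysis a model of 12-month neuropathic pain on the end-of-treatment evoked-pain value (or the change), with the baseline value of the same site and modality as a named covariate. This replaces the unadjusted correlation. Flag thresholds at 0°C or 50°C and ratings at the floor, and report those subjects as a separate group. Add a sensitivity analysis restricted to sites with a measurable pain threshold at baseline.

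The cost is wording and one or a few covariates. The restricted analysis loses power (about 0.70 at a 20% share and 0.57 at 40%, both shares assumed), which is why it should not be the main one.

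Baseline adjustment is not a complete cure. Table 1 in the Background gives a test-retest coefficient of 0.50 for both hot and cold pain thresholds in people with spinal cord injury. With a baseline that noisy, the end-of-treatment value still carries some information about true baseline sensitivity, so the near-exact recovery in the simulation is a best case. Fitting the same model in the sham arm alongside would help to show how much of any association reflects this or spontaneous recovery.
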